#### 9.4.10 Change from Baseline

$$\text{Baseline Change}_i = \text{Value}_i - \text{Baseline}$$

Change from baseline is post-baseline assessment subtracted by the baseline assessment.

#### 9.4.11 Percent Change from Baseline

$$\text{Baseline Change} (\%)_i = (\text{Baseline Change}_i / \text{Baseline})$$

Percent change from baseline is calculated as the change from baseline divided by the baseline assessment and multiplied by 100%.

#### 9.4.12 Change from Baseline on the Log Scale

$$\begin{aligned} \log \text{Baseline Change}_i &= \log \text{Value}_i - \log \text{Baseline} \\ &= \log \left( \frac{\text{Value}_i}{\text{Baseline}} \right) \end{aligned}$$

The change from baseline on the log scale is calculated as  $\log(\text{post-baseline assessment})$  subtracted by the  $\log(\text{baseline assessment})$ . It is also mathematically equivalent to the log of the ratio of the post-baseline assessment divided by the baseline assessment.

#### 9.4.13 Geometric Mean Ratio and Percent Change

For PD hormone variables (Section 5.3.2), the geometric mean ratio (GMR) and percent change from baseline will be calculated by cohort and dose level. The GMR is derived from the natural logarithm of the post-baseline value divided by the baseline value [ $\log(\text{post-baseline}/\text{baseline})$ ]. The GMR is the exponential function of the mean of  $\log(\text{post baseline}/\text{baseline})$ . The 95% CI of GMR is the exponential function of the 95% CI of the mean [ $\log(\text{post baseline}/\text{baseline})$ ]. The percent change is derived as  $100 \times (\text{GMR} - 1)$ . The 95% CI of percent change is  $100 \times (95\% \text{ CI of GMR} - 1)$ .

#### 9.4.14 Responder Definitions

The second secondary efficacy and exploratory variables are proportions of responders based on serum PD assessments and GC dosing. Indicator variables for each responder criteria are defined in [Table 5](#).

**Table 5** Responder Definition by Endpoint

Endpoint	Definition	
Composite: Proportion of subjects who achieve reduction in A4 OR reduction in GC dosing (Cohorts 1 through 3) at a postbaseline visit	1	Reduction in A4 OR reduction in GC Dose
	0	(no reduction in A4 AND no reduction in GC Dose) OR missing
Proportion of subjects with elevated baseline A4 who achieve a reduction in A4 at a post-baseline visit	1	Baseline A4 > ULN AND reduction in A4
	0	Baseline A4 ≤ ULN OR no reduction in A4 OR missing
Any reduction at a postbaseline visit	1	Reduction from baseline
	0	No reduction from baseline OR missing
≥ 50% reduction at a postbaseline visit	1	≥ 50% reduction from baseline
	0	< 50% reduction from baseline OR missing
≤ ULN at a post-baseline visit	1	≤ ULN
	0	> ULN OR missing

#### 9.4.15 Study Drug Exposure Variables

##### 9.4.15.1 Nominal Tildacerfont Dose (mg)

The nominal tildacerfont dose is collected in “Pediatric weight-based dosing (mg)” question in the Drug Accountability Cohort 1 eCRF form and the Drug Accountability eCRF form, respectively.

##### 9.4.15.2 Tildacerfont Dose Adjusted for Body Weight (mg/kg)

For a given dispensation visit, the concurrently measured weight as measured in the Vital Signs CRF form will be used to calculate the tildacerfont dose adjusted for body weight by dividing the nominal tildacerfont dose (mg) by weight (kg) ([Table 13](#)).

#### 9.4.16 Prior, Concomitant and Post treatment Medications

Prior medication is any medication that is taken within a year prior to the first study drug dosing.

A concomitant medication (CM) is any medication the subject is taking, other than tildacerfont during the study. CMs are medications: that are continued from Screening and continued after the first study drug dosing, or with start dates or stop dates within the first dose date through last dose date + 24 hours, missing CM end date, or ongoing within the study.

Post medications are any medication taken after the last study drug dose date + 24 hours, missing CM end date, or ongoing.

##### 9.4.16.1 Prohibited Concomitant Medications

Prohibited and cautionary concomitant medications are those medications with their potential for metabolic interactions with tildacerfont. Specific definitions are in [Table 14](#), which provides a non-exhaustive list of medications.

##### 9.4.17 Glucocorticoid Therapy

GC therapies are concomitant medications that fall under the Anatomical Therapeutical Chemical (ATC) classification is “Systemic Hormonal Preparations, Excl. Sex Hormones and Insulins” or “Glucocorticoids” as collected in the Concomitant Medication eCRF form.

##### 9.4.17.1 Glucocorticoid Dose in Hydrocortisone Equivalents

[Table 6](#) defines the potencies of various GCs relative to HC in treating CAH. These conversion factors will be used to standardize and determine whether a subject's daily GC dose satisfies study eligibility criteria and provide general guidelines for GC tapering.

**Table 6      Relative Potencies of Glucocorticoids in Hydrocortisone Equivalents**

Glucocorticoid	Potency in CAH (HCe)
HYDROCORTISONE	1
PREDNISONE	4
PREDNISOLONE	5
PREDNISOLONE SODIUM PHOSPHATE	5
METHYLPREDNISOLONE	5
TRIAMCINOLONE	5
DEXAMETHASONE	70
CORTEF	1
HYDROCORTISONE (ALKINDI SPRINKLES)	1
CORTISONE ACETATE	0.8

#### *9.4.17.2 Glucocorticoid Body Surface Area Based Dose*

The baseline GC BSA-based dose is calculated as the GC dose ([Section 9.4.17.1](#)) divided by the body surface area ([Section 9.4.7](#)) at the corresponding time point, rounded to two decimal places.

#### *9.4.17.3 Glucocorticoid Dose at Visit*

Based on the GC therapies collected in the A4-based GC Dose Adjustment eCRF form, GC dose at visit is collected under the question, “Total GC Dose (mg)”.

#### *9.4.17.4 Baseline Glucocorticoid Dose*

The GC dose at Day 1 (baseline) is assumed to be the same dose at Week 4.

### *9.4.18 Adverse Events*

AEs are any untoward medical occurrence in a subject participating in a clinical trial with onset date from the signing of the informed consent/assent until the end of the follow up period.

TEAEs are defined as any AEs, regardless of relationship to study drug, which have an onset or worsening in severity on or after the first dose of study drug until 30 days after the final dose of study drug (Follow-up visit). For AEs that occur on the date of the first dose of study drug, the time of onset (before or after intake of study drug) will be specified and used for comparison. If a subject discontinues study drug but remains in the study, AEs with onset date after 30 days of last dose of study drug until the end of the follow up period will be considered post-treatment adverse events.

Related TEAEs are those reported by investigators as possibly related, probably related, or definitely related to the study drug.

AESIs are events that do not meet SAE criteria but must be monitored on an ongoing basis as defined in the Study Protocol Section 7.2.8 and identified in the AE eCRF page.

Serious AEs (SAEs) are defined in the Study Protocol Section 7.2.6 and identified in the AE eCRF page.

Dose-limiting toxicities (DLTs) are defined as a Common Terminology Criteria for Adverse Events (CTCAE) Grade 3 or higher TEAE that is also considered at least possibly related to study drug.

Suspected unexpected serious adverse reactions is an AE that is serious, related to study drug, and is not expected in the targeted disease (classic CAH).

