6.1.2. Safety Monitoring and Stopping Rules for Abnormal Liver Chemistry Measurements

The following was adapted in accordance with the non-binding recommendations contained within the FDA Guidance for Industry Drug-Induced Liver Injury: Pre-marketing Clinical Evaluation, from the U.S. Department of Health and Human Services in July 2009.

Special attention is paid to potential liver toxicity because tildacerfont was identified as a bile salt export pump (BSEP) inhibitor based on pre-clinical studies. Although in vitro BSEP inhibition does not reliably predict in vivo BSEP inhibition, Spruce believes that the pre-clinical findings warrant ongoing clinical monitoring ([Jonathan 2018](#)). Consequently, abnormal transaminase results will be assessed as follows.

If stopping criteria are met at any time during the Treatment Period, study drug should be held until confirmatory testing of the transaminase, with additional measurements of total bilirubin, alkaline phosphatase (ALP), complete blood count (CBC) with differential and international normalized ratio (INR), is performed. Ideally, confirmatory testing would be performed within 48 hours of the initial receipt of the abnormal result. Confirmation testing through the central lab is preferred, but local laboratory testing may be necessary in certain circumstances. Confirmed cases meeting stopping criteria will be reported as an AESI and in cases where a possible Hy's Law case is present, the event should also be reported as an SAE. [Table 4](#) outlines specific stopping criteria for this study.

Table 4. Stopping Criteria and Increased Monitoring for Liver Chemistry Elevations

Criteria		Actions
Participant has symptoms (new or worsening) believed to be related to liver injury or hypersensitivity ¹		Hold study drug, measure liver chemistry (AST/ALT/ALP), CBC with differential, total bilirubin, total bile acids and INR as soon as possible and notify Sponsor.
ALT 3x ULN		Discontinue study drug and notify Sponsor.
ALT 3x ULN	AND total bilirubin 2x ULN (>35% direct bilirubin) ²	Discontinue study drug and notify Sponsor. Possible Hy's Law case— report as an AESI and SAE .
	AND INR >1.5	Discontinue study drug and notify Sponsor. Possible Hy's Law case— report as an AESI and SAE .
Total Bile Acids >5xULN		Discontinue study drug and notify Sponsor.

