6.1.5. Suicidality Stopping Criteria

Tildacerfont is a central nervous system (CNS)-active drug. Some CNS-active drugs may be associated with an increased risk of suicidal ideation in certain populations. Although tildacerfont has not been shown to be associated with an increased risk of suicidal thinking or behavior in past clinical studies, participants will be monitored for such events during this study using the C-SSRS. Any participant who exhibits Suicidal Behavior or Suicidal Ideation in their responses on the C-SSRS, will have study drug immediately discontinued and should be evaluated by a psychiatrist. This safety finding will be considered an AESI if it is not an SAE (e.g., requiring hospitalization) (see [Section 7.2.8](#)).

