6.1.6. Depression or Anxiety Stopping Criteria

Participants will be monitored for depression and anxiety during the study using the Patient Reported Outcomes Measurement Information System (PROMIS) Pediatric SF (Short Form) v2.0, the PROMIS Parent-Proxy SF (Short Form) v2.0, or the Survey of Well-Being of Young Children (SWYC). The questionnaire used will depend upon the participant's age. Any participant who develops severe depression or anxiety (CTCAE Grade 3 or higher), as assessed by the Investigator, will require study drug discontinuation and appropriate follow-up. This will be considered an AESI and if seriousness criteria are met, also reported as an SAE (e.g., requiring hospitalization) (see [Section 7.2.8](#)).

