7.2.6. Serious Adverse Event Reporting

Throughout the study, the Investigator is to report all SAEs, regardless of suspected causality, to the Sponsor within 24 hours of learning of its occurrence using the SAE Report Form. AESIs (see [Section 7.2.8](#)) will also be reported in the electronic data capture (EDC) system and on the SAE Report Form and must be clearly differentiated from SAEs. Completion guidelines are provided in the Investigator Site File. The Investigator must assess and record the relationship of each event to study drug. Any SAE experienced after the follow-up period should be reported to the Sponsor only if the Investigator suspects a causal relationship to the study drug.

Recurrent episodes, complications, or progression of the initial SAE, regardless of when they occur, must be reported as follow-up to the original episode within 24 hours of the Investigator receiving the follow-up information. Follow-up information will also be captured in the EDC system and should describe whether the event resolved or continues, if and how it was treated, and whether the participant continued or withdrew from study participation. An SAE occurring at a different time interval or otherwise considered completely unrelated to a previously reported SAE should be reported separately as a new event.

The Sponsor will ensure that all SUSARs, determined based on the Reference Safety Information in the most recent version of the IB at the time of the event, will be reported to the FDA and to all Institutional Review Boards (IRBs)/Ethics Committees (ECs) overseeing the conduct of the study, in accordance with FDA 21 CFR 312.32.

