7.2.8. Adverse Events of Special Interest

AESIs are those AEs (independent of seriousness criteria) that are of specific concern to this study and for which ongoing monitoring and communication with the Investigator and Sponsor may be appropriate. These events will be reported on the SAE Report Form, allowing for the collection of additional information, as warranted. The following may be considered AESIs for this study:

- Significant liver chemistry changes that do not satisfy study drug stopping rules (see [Section 6.1.2](#)). Cases of Hy's Law should be reported as an AESI and SAE.
- Suicidality as indicated by responses on the C-SSRS (see [Section 6.1.5](#) regarding study stopping criteria).
- Depression or anxiety that is moderate or severe (CTCAE Grade 2 or higher), as assessed by the Investigator (see [Section 6.1.6](#) regarding study drug stopping criteria for depression or anxiety). This will be reported as an AESI and if seriousness criteria are met, reported as an SAE.
- Adverse events of adrenal insufficiency are considered AESIs and will be reported on a separate Adrenal Insufficiency Form. Additionally, symptoms of adrenal insufficiency will be reported as SAE if they necessitate parenteral GC administration by a health care professional and two of the following criteria occur or are met: hypotension (systolic blood pressure <90 mmHg); nausea or vomiting; severe fatigue; documented hyponatremia, hyperkalemia, or hypoglycemia. If hospitalization was required or the event of adrenal insufficiency is deemed to be an important medical event, life-threatening, or results in a persistent or significant disability/incapacity or death, it should also be reported as an SAE.
 - For SAEs of adrenal insufficiency, records from the office of the health care provider, emergency facility or hospital should be obtained as source documents to provide the following information:
 - Was stress dosing employed prior to the adrenal insufficiency event? If yes, what were the GC dose and duration of dosing and the cause for stress dosing prior to seeking medical attention?
 - What type, dose and route of parenteral GC was administered and the duration of administration?
 - What concomitant medications were administered?
 - What clinical laboratory results are available?
 - What AEs occurred?
 - What was the duration of stay if admitted to the hospital?
 - What was deemed to be the inciting factor leading to adrenal crisis?

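### SAP 9.4.18 restricts AESIs to non-serious events, against the Protocol 7.2.8 definition it cites, and the Hy's law listing in SAP 14.2 does not match Protocol Table 4

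*SAP*

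**What the plan says.** **AESI definition.** SAP Section 9.4.18 says "AESIs are events that do not meet SAE criteria but must be monitored on an ongoing basis as defined in the Study Protocol Section 7.2.8". The sentence ends by saying that these events are "as defined in the Study Protocol Section 7.2.8 and identified in the AE eCRF page". Protocol Section 7.2.8, the section cited, says instead that "AESIs are those AEs (independent of seriousness criteria) that are of specific concern to this study". The definition feeds two outputs in SAP Section 14.1: a separate AESI listing and an AESI row in the overall AE summary. Protocol Section 8.3.4.2 also plans an AESI listing.

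**Hy's law listing.** SAP Section 14.2 lists subjects who concurrently meet ALT >3x ULN, AST >3x ULN and total bilirubin >2x ULN. Protocol Table 4 (Section 6.1.2) identifies a possible Hy's law case by either of two routes: ALT 3x ULN with total bilirubin 2x ULN and more than 35% direct bilirubin, or ALT 3x ULN with INR >1.5. For both routes the instruction is to "report as an AESI and SAE". Protocol Section 8.3.4.3 plans no Hy's law listing.

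**Precedence and declared changes.** SAP Section 4 makes the SAP text govern where the two documents disagree on planned analyses, and sends changes to Section 15. Section 15 covers the PD population, the elevated-baseline PD set, 11-KT, GC dosing frequency and exposure. It mentions neither AESIs nor Hy's law.

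**The concern.** Safety is the primary objective, and the AESI outputs are where a reader looks for the liver, psychiatric and adrenal events that the protocol singles out. A definition that excludes serious events would take the gravest of them out of those outputs. A reader who trusted the AESI row alone would see too few.

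The Hy's law listing has a similar weakness. A reader would expect it to show the cases that the protocol calls possible Hy's law, but it is built from different criteria and the SAP does not say why.

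**Working it through.** The documents give no figure for this point, so the check is a comparison of texts followed by a count of logical patterns.

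**Step 1: AESI and SAE, category by category (Protocol 7.2.8).**

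| Category | What the protocol says | Serious event under the literal SAP wording |
|---|---|---|
| Liver / Hy's law | 7.2.8 and Table 4: report as both | Not an AESI |
| Depression or anxiety | 6.1.6: "This will be considered an AESI and if seriousness criteria are met, also reported as an SAE"; 7.2.8 agrees | Not an AESI |
| Adrenal insufficiency | 7.2.8: an AESI, with stated conditions for also reporting it as an SAE | Not an AESI |
| Suicidality | 6.1.5: "This safety finding will be considered an AESI if it is not an SAE" | Not an AESI; agrees with 6.1.5 |

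The SAP wording conflicts with explicit dual reporting in 3 of 4 categories. Of the two possible-Hy's-law routes in Table 4, both are AESIs under the protocol and neither is under the literal SAP wording.

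**Step 2: one sentence, two rules.** If programming follows the first half of the SAP sentence, serious AESIs are excluded. If it follows the AE eCRF page, they are kept wherever the investigator has identified them as AESIs. The two rules give different counts as soon as one serious AESI occurs.

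**Step 3: Hy's law criteria.** Inputs, from Table 4 and SAP 14.2:
- ALT raised or not (2 levels)
- AST raised or not (2)
- bilirubin not raised, raised with direct fraction ≤35%, or raised with direct fraction >35% (3)
- INR >1.5 or not (2)

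Total patterns: 2 × 2 × 3 × 2 = 24.

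- Protocol-positive = ALT and (bilirubin raised with direct >35%, or INR >1.5). With ALT raised, each AST level has 3 patterns with INR raised and 1 with INR not raised, so 4 × 2 = 8.
- SAP-positive = ALT and AST and bilirubin raised = 1 × 1 × 2 × 2 = 4.
- In both: direct >35% with either INR level (2), plus direct ≤35% with INR raised (1) = 3.
- Missed by the SAP: 8 − 3 = 5. Four have AST not raised. The fifth has ALT, AST and INR raised but bilirubin not raised.
- Added by the SAP: 4 − 3 = 1 (ALT, AST and bilirubin raised, direct ≤35%, INR not raised).

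An example that needs no INR: ALT 4x, AST 2x and bilirubin 2.5x ULN with more than 35% direct meets Table 4 and is not listed under SAP 14.2.

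The counts depend on coding. If the direct fraction is a separate yes/no flag there are 32 patterns: 10 protocol-positive, 3 captured, 7 missed and 1 added. The conclusion is the same.

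The extracted Table 4 shows no comparison sign for ALT or bilirubin, so > against ≥ is not compared.

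**The case against.** On AESIs, the best defence is that the reference to the AE eCRF page would keep serious AESIs if the outputs are built from it. The protocol also gives the SAP wording some support. Section 6.1.5 treats suicidality as an AESI only when it is not an SAE, and Section 7.2.6 says that AESIs "must be clearly differentiated from SAEs". The first part stands as a limit on the effect: nothing is lost if the eCRF identification is used. The suicidality clause also stands, but for one category only. The 7.2.6 phrase concerns how events are marked when reported. It cannot mean that the two classes exclude each other, because Table 4 and 7.2.8 require both for Hy's law.

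The protocol is not fully consistent on liver events either. Section 7.2.8 names "Significant liver chemistry changes that do not satisfy study drug stopping rules", while Section 6.1.2 makes confirmed cases that do meet the stopping criteria AESIs. That needs reconciling, but it does not support a restriction by seriousness.

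On Hy's law, Table 4 is a stopping and reporting rule and SAP 14.2 is an additional laboratory listing. Investigators report possible cases as AESI and SAE whatever the listing shows, and Protocol Section 1.3 provides a Hepatic Adjudication Committee. Leaving out the direct-bilirubin condition only widens the listing, and footnote 2 of Table 4 itself acts on ALT and total bilirubin when fractionation is not immediately available. INR is scheduled at Screening only, although Section 6.1.2 requires it at confirmatory testing and Section 6.1.3 during liver follow-up. All of this stands. It limits the consequence but does not make the two sets of criteria agree.

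**Conclusion.** Both parts hold, and both should be corrected. The AESI definition is the main one: it is a wrong stated rule in a document that governs the analysis, contrary to the section it cites and not declared in Section 15. The effect is confined to the AESI listing and the AESI summary row in SAP 14.1. It arises only if the literal wording is followed and at least one serious AESI occurs. The case report forms are not among the documents, so how AESIs are marked there is not known.

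The Hy's law listing is the lesser part. Reading concurrently in its natural sense, as all three criteria together, it misses every Table 4 case with AST not above 3x ULN and every ALT-with-INR case with bilirubin not above 2x ULN.

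A reader might infer three stronger things that the documents do not support:
- That serious AESIs vanish from the safety report or that the primary endpoint changes. They remain in the AE, SAE and TEAE outputs, and the laboratory values remain in the listings.
- That 5 missed patterns of 8 is a miss rate. The patterns carry no frequencies and say nothing about how many participants would be affected.
- That the listing is an undeclared change to a protocol analysis. The protocol plans no such listing, so it is an addition. The complaint about Section 15 therefore applies to the AESI definition, not with equal force here.

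No view is taken on which Hy's law criteria are clinically right.

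**What to change.** 1. **SAP 9.4.18.** Delete the restriction to events that do not meet SAE criteria. State that AESIs are those in Protocol 7.2.8 regardless of seriousness, identified by the AESI flag on the AE eCRF, and that a serious AESI appears in both the AESI and SAE outputs. Without the restriction, the definition and the flag no longer conflict on seriousness.
2. **Protocol.** The sponsor should reconcile 6.1.5 with 7.2.8 for suicidality and 6.1.2 with 7.2.8 for liver events. Until the first is settled, the new SAP sentence should say how a serious suicidality event is handled, because 6.1.5 as written would not count it as an AESI.
3. **Cross-reference.** SAP 9.4.18 cites Protocol 7.2.6 for the SAE definition. That section covers reporting, and the definition is in 7.2.2. This is a clerical correction to make at the same time.
4. **SAP 14.2.** List subjects who meet either Table 4 route, using any triggered or local INR in the database, with AST and the direct bilirubin fraction shown as columns. Otherwise keep the present criteria and state why they differ from Table 4.

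The SAP changes cost some wording and one listing program. No new data collection is needed, since direct bilirubin is already in the scheduled chemistry panel. The downside is that the INR route will be only as complete as the entry of triggered or local results into the database.

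### SAP 9.4.18 restricts AESIs to non-serious events, contrary to the Protocol 7.2.8 definition it cites, so the AESI listing and AESI summary row, read literally, omit the serious ones

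*SAP*

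**What the plan says.** SAP 9.4.18 gives the analysis definition: "AESIs are events that do not meet SAE criteria but must be monitored on an ongoing basis". The same sentence then points to Protocol 7.2.8 for the definition and to the AE eCRF page for identification.

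Protocol 7.2.8 opens differently: "AESIs are those AEs (independent of seriousness criteria) that are of specific concern to this study". Its four categories are liver chemistry changes, suicidality, depression or anxiety, and adrenal insufficiency. Three of them carry an explicit rule for serious events:

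- Liver: "Cases of Hy's Law should be reported as an AESI and SAE".
- Depression or anxiety of Grade 2 or higher: "This will be reported as an AESI and if seriousness criteria are met, reported as an SAE". Section 6.1.6 repeats this for Grade 3 or higher: "This will be considered an AESI and if seriousness criteria are met, also reported as an SAE".
- Adrenal insufficiency: "Adverse events of adrenal insufficiency are considered AESIs and will be reported on a separate Adrenal Insufficiency Form". In addition, "symptoms of adrenal insufficiency will be reported as SAE if they necessitate parenteral GC administration by a health care professional" and two further listed criteria are met. Hospitalization and the other usual seriousness criteria also make the event an SAE.

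SAP 14.1 uses the AESI definition in two outputs: a separate listing, and a line (number and percentage) in the overall AE summary.

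**The concern.** The SAP cites a protocol section and then states a condition that the section rejects. SAP section 4 resolves SAP-protocol conflicts over planned analyses in the SAP's favor. A programmer who follows SAP 9.4.18 as written therefore has grounds to filter serious events out of the AESI outputs.

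Those outputs exist to bring the events of particular interest together in one place. Under the literal wording they would hold the milder liver, mood and adrenal insufficiency events and leave out the Hy's Law cases, the serious depression and the adrenal crises. A reader of the study report who took the AESI row as the count of such events would see too low a figure. Safety is the primary objective and this is the drug's first pediatric study, so the AESI table should mean what the protocol says it means.

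**Working it through.** The plan gives no AESI rate and none is assumed here. The check is a comparison of texts, followed by simple arithmetic for the size of the effect.

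**Step 1. Does the SAP condition contradict the protocol, category by category?**

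| Protocol 7.2.8 category | Protocol status of a serious event | Status under the SAP 9.4.18 wording |
|---|---|---|
| Liver (Hy's Law cases) | AESI and SAE (7.2.8; Table 4) | not an AESI |
| Depression or anxiety | AESI and SAE (7.2.8; 6.1.6) | not an AESI |
| Adrenal insufficiency | AESI and SAE (7.2.8) | not an AESI |
| Suicidality | mixed: 7.2.8 has no dual rule, and 6.1.5 makes it an AESI only when it is not an SAE | not an AESI |

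The contradiction is explicit in 3 of 4 categories. For suicidality the SAP agrees with Protocol 6.1.5, so that category is not counted.

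**Step 2. Is it a declared change?** SAP section 15 lists five changes from the protocol: the PD set, the elevated-baseline PD set, 11-KT, GC dosing frequency, and exposure. None concerns AESIs.

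**Step 3. Which outputs use the definition?** Two, both in SAP 14.1: the AESI listing and the AESI row of the overall summary. SAP section 14 presents safety analyses by adult-equivalent dose level, and 14.1 counts by enrollment experience. The relevant denominator is therefore the number of enrollment experiences at a dose level, not the size of a cohort.

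**Step 4. Size.** Let n be that denominator. If an enrollment experience has only serious AESIs, the literal wording removes it from the numerator and the percentage falls by 100 × 1/n points. If it also has a non-serious AESI, the percentage does not change, but the listing still loses the serious record.

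- 200 mg BID: Cohorts 4, 6 and 7, planned n = 5 + 5 + 5 = 15. 100 × 1/15 = 6.7 points.
- A dose level with n = 5, such as 50 mg QD if given only in Cohort 1: 100 × 1/5 = 20.0 points.

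These are planned numbers. Protocol 1.2.3 already reports 30 pediatric participants in Cohorts 1–3 against a planned maximum of 25, and re-enrolled participants add enrollment experiences, so the actual n may differ.

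**Step 5. If the eCRF flag alone drives the outputs.** Sites flag AESIs under Protocol 7.2.8, so serious ones carry the flag and the loss is 0.

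**The case against.** The strongest reply is that the SAP sentence does not stop at the non-SAE condition. It also invokes Protocol 7.2.8 and the AE eCRF page, and nothing in the SAP describes deriving AESIs as flagged and not serious. On that view the phrase is a loose paraphrase with no effect on any table. The protocol has similar looseness: 7.2.6 asks for AESIs to be clearly distinguished from SAEs when reported, and 6.1.5 ties AESI status to non-seriousness for suicidality.

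Part of this stands. With flag-only programming there is no loss. It does not remove the problem, because the sentence states the non-serious condition alongside the flag. One text then permits two different counts. Section 7.2.6 concerns report forms rather than what an AESI is, and 6.1.5 covers one category of four.

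A reader might also infer more than the documents support:

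- *That serious safety data would be lost.* They would not. SAP 14.1 lists all AEs and separately lists and tabulates SAEs.
- *That safety decisions would suffer.* The primary endpoint is AEs and SAEs. Cohort stopping (Protocol 6.1.8) counts participants who meet individual stopping criteria. Protocol 6.1.7 sends SAEs to the DMC whatever their AESI label.
- *That GC lowering makes missed adrenal insufficiency a study-wide issue.* The A4 algorithm reduces GC only at A4 at or below ULN, and raises it above 1.5 × ULN. Cohorts 4–9 have no GC adjustment in the 4-week period, and the extension has its own SAP. Within this SAP the argument reaches only Cohorts 1–3 from Week 4.
- *That the excluded set cannot be identified, because "Serious AEs (SAEs) are defined in the Study Protocol Section 7.2.6 and identified in the AE eCRF page" cites the reporting section rather than 7.2.2.* This is a clerical slip; the eCRF identifies the SAEs.
- *That the liver texts conflict.* The 7.2.8 liver bullet refers to 6.1.2, which makes confirmed stopping cases AESIs. The two can be read together.

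**Conclusion.** The point holds as a drafting contradiction in the SAP. The definition in 9.4.18 is wrong against the protocol section it cites, it is undeclared, and under SAP section 4 it would prevail. Read literally, it makes two planned outputs incomplete for 3 of the 4 AESI categories.

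The consequence is mislabelled and undercounted AESIs, not missing safety information. The effect on the AESI percentage ranges from zero, if the eCRF flag alone is used, to 100/n points for each enrollment experience whose only AESI is serious. The size rests on planned dose-level numbers and on sites flagging serious AESIs as the protocol instructs. It should be corrected before database lock, but it does not threaten the study's conclusions.

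**What to change.** Replace the AESI sentence in SAP 9.4.18 with: *AESIs are AEs, whether or not they meet SAE criteria, as defined in Protocol Sections 6.1.2 and 7.2.8 and identified in the AE eCRF page; serious AESIs are included in both the AESI and SAE outputs.*

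As housekeeping in the same section, change the SAE cross-reference from Protocol 7.2.6 to 7.2.2.

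The cost is one rewritten SAP sentence and one corrected reference, with no new data. The small downside is that some events will appear in both the AESI and SAE rows, which a table footnote can state.

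The 7.2.8 liver bullet, Table 4 and the suicidality sentence in 6.1.5 could be tidied at a future protocol amendment. Protocol changes need IRB approval (Protocol 9.10), and this fix does not depend on them.
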